## 6 Objectives

QMS Document Name: Statistical Analysis Plan	Page 10 of 29
QMS No (include version ref): STF-015-GL.02	Document date: 09JUL2019
CONFIDENTIAL	

### **6.1 Primary Objective**

To evaluate the safety of ALM-488 administered by intravenous (IV) infusion to subjects undergoing head and neck surgery.

### **6.2 Secondary Objectives**

- To characterize the PK of ALM-488 in subjects undergoing head and neck surgery.
- To determine the dose of ALM-488 needed to generate an adequate fluorescence signal in nerves.
- To evaluate the effect of timing of administration of ALM-488 relative to surgery (e.g., up to 5 hours before surgery) on adequacy of fluorescence nerve labeling.

### **6.3 Exploratory Objectives**

Exploratory objectives will evaluate early evidence of efficacy. These are:

- To evaluate the ability of imaging techniques (i.e. camera systems) to distinguishing nerve tissue from non-nerve tissue.
- To evaluate the intensity of signal of fluorescence relative to nerve diameter.
- To evaluate the intensity of signal of fluorescence when there is overlying tissue.
- To assess the depth of fluorescence penetration when there is overlying non nerve tissue.
- To evaluate surgeon confidence and operative time with a surgeon rating scale.

## **7 Endpoints**

### **7.1 Safety Endpoints**

The endpoints to assess the safety of ALM-488 include:

- Adverse Events (TEAEs)
- Vital signs
- Clinical laboratory evaluations
- ECGs
- Physical examinations

Summaries of AEs will be based on Treatment Emergent Adverse Events (TEAEs) and will be summarized separately for each device and each of the Cohorts A1-A6, B1 and B2, as well as overall for Cohort A and Cohort B.

Vital signs, labs, ECGs, and physical exams will be summarized separately for each of the Cohorts A1-A6, B1 and B2, as well as overall for Cohort A and Cohort B.

### **7.2 Secondary Endpoints**

The endpoints to characterize the PK of ALM-488 will be fully described in the PK SAP.

The endpoints to determine the dose of ALM-488 needed to generate an adequate fluorescence signal in nerves include the following:

- Timing of administration of ALM-488 relative to surgery

QMS Document Name: Statistical Analysis Plan	Page 11 of 29
QMS No (include version ref): STF-015-GL.02	Document date: 09JUL2019
CONFIDENTIAL	

- Dose
- Intensity (signal-to-background ratio- SBR)
- Surgeon rating scale

The endpoints to determine the dose of ALM-488 needed to generate an adequate fluorescence signal in nerves will be summarized for each of Cohorts A1-A6, as well as overall for Cohort A.

The endpoints to evaluate the effect of timing of administration of ALM-488 relative to surgery on adequacy of fluorescence nerve labeling include the following:

- Timing of administration of ALM-488 relative to surgery
- Time from injection to skin incision
- Intensity (SBR)
- Surgeon rating scale

The endpoints to evaluate the effect of timing of administration of ALM-488 relative to surgery on adequacy of fluorescence nerve labeling will be summarized for each of Cohorts B1 and B2, as well as overall for Cohort B.

### 7.3 Exploratory Endpoints

To evaluate the ability of imaging techniques (i.e. camera systems) to distinguishing nerve tissue from non-nerve tissue, the following endpoints will be evaluated:

- Ability to detect fluorescence will be studied by determining an optimal cut-off using Youden index and receiver operating characteristic ROC curve analysis.

This endpoint will be summarized separately for each device and each of the Cohorts A1-A6, B1 and B2, as well as overall for Cohort A and Cohort B.

To evaluate the intensity of signal of fluorescence relative to nerve diameter, the following endpoints will be evaluated:

- Intensity (signal-to-background ratio SBR)
- nerve diameter

These endpoints will be plotted against each other, separately for each device and each of the Cohorts A1-A6, B1 and B2, as well as overall for Cohort A and Cohort B.

To evaluate the intensity of signal of fluorescence when there is overlying tissue, the following endpoints will be evaluated:

- Signal-to-background ratio)

This endpoint will be summarized separately for images and each of the Cohorts A1-A6, B1 and B2 as well as overall for Cohort A and Cohort B.

To evaluate surgeon confidence and operative time with a surgeon rating scale, the following endpoints will be evaluated:

- Surgeon confidence will be captured via the surgeon rating scale (1=do not see nerve compared to WLR, 2=see nerve less well compared to WLR, 3=See nerve equally well

QMS Document Name: Statistical Analysis Plan	Page 12 of 29
QMS No (include version ref): STF-015-GL.02	Document date: 09JUL2019
CONFIDENTIAL	

compared to WLR, 4=See nerve better compared to WLR, 5=See nerve much better compared to WLR) for each image.

- For each surgery, the following yes/no question will be asked: “Outside of a clinical trial setting with all the required extra documentation, would this technology have saved you operative nerve-dissecting time compared to WLR?”

Surgeon confidence will be summarized by image, while time saving (yes/no) will be summarized by patient.

Surgeon confidence will be summarized for each device and each of the Cohorts A1-A6, B1 and B2, as well as overall for Cohort A and Cohort B.

Time saving (yes/no) will be for each of the Cohorts A1-A6, B1 and B2, as well as overall for Cohort A and Cohort B.

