#### **4.1 Sample Size Estimation**

The primary objective of this study is to evaluate the safety of ALM-488 administered by intravenous (IV) infusion to subjects undergoing head and neck surgery.

At each dose level, a cohort of 3 subjects will be enrolled for safety and tolerability evaluation. If there are no subjects with a DLT at a given dose level, new subjects will be enrolled at the next dose escalation level. If there are  $\geq 1$  subjects having any DLT, the enrollment to that specific dose and dose escalation will stop. New subjects will be enrolled at the next dose de-escalation level. There will be a minimum of 3 cohorts. Given that there will be 3-6 subjects for each dose level, 9-36 subjects will be needed for the dose escalation/de-escalation cohorts.

It is anticipated that the proposed dose range (100-1000mg) is expected to yield optimal imaging performance, with an initial starting dose of 100mg that has been selected based on supportive nonclinical testing. If the 100 mg dose is found to provide adequate fluorescence imaging of nerves, a dose de-escalation schedule will be followed to ensure that the lowest effective dose is determined. If imaging at starting first de-escalated dose (75 mg) becomes less adequate compared to 100mg as determined by the SRC, then imaging at dose escalation schedule will resume - beginning at 200mg. The Optimal Dose will be determined by the SRC as the lowest possible dose and toxicity profile that achieves adequate imaging performance of nerves using WLR combined with FL.

The Dose Timing Cohort will use the Optimal Dose as defined by the SRC following completion of the Dose Escalation/De-Escalation cohorts. Subjects in the Dose Timing phase will be administered ALM-488 at two planned operative times before surgery to assess the impact of timing of administration on fluorescence image quality. This phase will consist of 2 cohorts, 6 subjects/cohort: (1) dose administration 3-5 hours in advance of surgery, (2) dose administration 1-3 hours in advance of surgery. A total of 12 subjects will be needed for the Dose Timing phase.

In summary, 9-36 subjects may be enrolled into the dose escalation/dose de-escalation cohorts and 12 subjects may be enrolled into the dose timing cohort. A total of 21-48 subjects may be enrolled into this study.

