### **13.1 Timing, Dose, Size and Intensity**

The efficacy endpoints pertaining to timing of administration, dose, and intensity (signal-to-background ratio SBR), along with the surgeon rating scale will be assessed throughout enrollment into Cohorts A1-A6 to determine the final dose for use in Cohorts B1 and B2. These efficacy endpoints will also be used to evaluate the effect of timing of administration of ALM-488 by comparison of Cohort B1 and B2. The following analyses are planned for these efficacy endpoints:

- For each Cohort, SBR will be averaged to get a single mean ratio per patient; then a paired t-test or Wilcoxon signed rank test will be used, as appropriate, to compare SBR between FL and WLR.
- SBR will be also listed by cohort type, and surgery type and device for both FL with WLR.
- Image intensity ratios will also be analyzed with repeated measures analysis of variance (RMANOVA) with timing, image, method (FL /WLR), and device (Zeiss/OnLume) as the repeated factors in the model.
- SBR for FL and WLR measurements will be plotted. Values to the right of the line will indicate that there is improved visualization with FL images and values to the left of the line will indicate that there is improved visualization with WLR images(Equal performance of FL versus WLR will be indicated by dashed line (slope = 1)].
- To further assess timing, Cohorts B1 and B2 will be compared. Image ratios will be averaged to get a single mean ratio per patient; then an unpaired t-test or Wilcoxon rank sum test will be used, as appropriate, separately for FL and WLR.

Paired t-tests will be used unless markedly non-normal data is observed including bimodal or other severe assumption violations; minor skewness is robust to the paired t-test and RMANOVA assumptions. If extreme skewness with outliers, or bimodal distributions are observed, then a Wilcoxon signed rank test will be used instead of a paired t-test and RMANOVA will be performed on the ranked data.

Similarly, unpaired t-tests will be used unless markedly non-normal data is observed including bimodal or other severe assumption violations; minor skewness is robust to the unpaired t-test assumptions. If extreme skewness with outliers, or bimodal distributions are observed, then a Wilcoxon rank sum test will be used instead.

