### **13.2 Surgical Imaging Worksheet/ Rating Scale**

Surgeon confidence will be captured via the surgeon rating scale (1=do not see nerve , 2=see nerve less well compared to WLR, 3=see nerve equally well compared to WLR, , 4=see nerve better compared to WLR, 5=see nerve much better compared to WLR ) for each image. Surgeon confidence will be summarized overall and by device, individual Cohorts (i.e., Cohorts: A, A1, A2, A3, A4, A5, A6, B, B1, B2) as well surgery type.

Image intensity ratios will also be correlated with the surgeon rating scale using Pearson correlation coefficients unless markedly non-normal data is observed including bimodal or other severe assumption violations; otherwise Spearman correlation coefficients will be used. Correlation coefficients will be presented overall and by device and by individual Cohorts (i.e., Cohorts: A, A1, A2, A3, A4, A5, A6, B, B1, B2).

A listing will be provided.

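### The surgeon rating, a secondary endpoint used in choosing the dose, is summarised by image with no stated per-patient summary, so one heavily imaged patient can dominate that summary in a cohort of 3 to 6

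*SAP*

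**What the plan says.** SAP Section 7.2 names the surgeon rating scale among the endpoints for the dose objective and again for the timing objective. Of the dose endpoints it says "The endpoints to determine the dose of ALM-488 needed to generate an adequate fluorescence signal in nerves will be summarized for each of Cohorts A1-A6", without naming the unit to be summarised. Section 13.1 says that timing, dose and SBR, "along with the surgeon rating scale will be assessed throughout enrollment into Cohorts A1-A6 to determine the final dose".

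The rating runs from 1 to 5 and is given for each image. The unit of summary is stated once, in Section 7.3, under the exploratory objective on surgeon confidence: "Surgeon confidence will be summarized by image, while time saving (yes/no) will be summarized by patient". Section 13.2 sets the breakdowns: "Surgeon confidence will be summarized overall and by device, individual Cohorts", and also surgery type. It mentions no step that reduces the ratings to one value per patient. Table 14.2.5.1 in Section 20.1 is a title only.

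SBR is handled differently. For the comparison of fluorescence with white light, Section 13.1 says "For each Cohort, SBR will be averaged to get a single mean ratio per patient", and it averages per patient again before comparing Cohorts B1 and B2.

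On cohort size, Section 4.1 says: "Given that there will be 3-6 subjects for each dose level, 9-36 subjects will be needed for the dose escalation/de-escalation cohorts". Section 5 admits a patient to the full analysis set with as little as one evaluable image. The available text sets no number of images per patient and no cap.

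**The concern.** The dose question is about patients: at a given dose, do patients get nerve visualisation that is good enough? A percentage of pooled images answers a different question. A patient with a long dissection, or with a nerve that fluoresces well and is photographed many times, counts for more than a patient with few images. In a cohort of three, the pooled figure can then say that ratings were mostly better than white light when most patients did not have that experience, or the reverse.

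The two imaging measures that feed the dose choice would also be on different footings, with SBR tested on one value per patient and the rating pooled over images. Nothing numeric limits the effect. SAP Sections 4 and 12 give no threshold for adequate fluorescence, and Section 4.1 leaves to the Safety Review Committee (SRC) whether imaging at 75 mg is less adequate than at 100 mg. That judgement may compare two cohorts of three, so the form of the summary matters.

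**Working it through.** **Cohort sizes (SAP Sections 4 and 4.1).** Three cohorts of 3 give 3 × 3 = 9, and six cohorts of 6 give 6 × 6 = 36, which reproduces the stated 9-36. The timing phase is 2 × 6 = 12, so the totals are 9 + 12 = 21 and 36 + 12 = 48, as stated. The relevant n is therefore 3 to 6 per dose cohort and 6 per timing cohort.

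**Weight of one patient in a pooled image summary.** Let one patient have k times as many images as each of the other n - 1 patients. That patient's share of the images is k/(k + n - 1). The effective number of patients (Kish) is (k + n - 1)²/(k² + n - 1). The documents give no image counts, so k is an assumption and a range is shown.

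| k | Share, n = 3 | Effective patients, n = 3 | Share, n = 6 | Effective patients, n = 6 |
|---|---|---|---|---|
| 1 | 33.3% | 3.00 | 16.7% | 6.00 |
| 2 | 2/4 = 50.0% | 2.67 | 2/7 = 28.6% | 5.44 |
| 3 | 3/5 = 60.0% | 2.27 | 3/8 = 37.5% | 4.57 |
| 5 | 5/7 = 71.4% | 1.81 | 5/10 = 50.0% | 3.33 |
| 10 | 10/12 = 83.3% | 1.41 | 10/15 = 66.7% | 2.14 |

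The patient holds more than half of the images once k exceeds n - 1: above 2 in a cohort of three, and above 5 in a cohort of six. One value per patient restores the k = 1 row whatever the image counts.

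**What this does to a reported percentage (image counts and ratings assumed).**

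- Three patients with 4, 4 and 12 images, and ratings of 4-5 on 25%, 25% and 100% of them. By image: (1 + 1 + 12)/20 = 70%. Patient average: (25 + 25 + 100)/3 = 50%. Only 1 of 3 patients has most images at 4-5.
- The same counts with 100%, 100% and 25%. By image: (4 + 4 + 3)/20 = 55%. Patient average: (100 + 100 + 25)/3 = 75%.
- Six patients, five with 4 images at 25% and one with 12 at 100%. By image: (5 × 1 + 12)/(5 × 4 + 12) = 17/32 = 53.1%. Patient average: (5 × 25 + 100)/6 = 37.5%.

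The gap is 20 points in either direction at n = 3, and 15.6 points at n = 6 with the same 3:1 ratio. With equal image counts the image-level percentage and the patient average agree.

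**The case against.** Several points on the other side stand.

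- **The by-image unit is stated only in Section 7.3.** Section 13.2 and the title of Table 14.2.5.1 do not state a unit, and Section 7.2 speaks only of cohorts. The gap for the secondary use is the absence of any per-patient summary.
- **Patient-level ratings are not missing.** Section 13.2 promises a listing, Section 20.2 includes the Surgical Imaging Worksheet listings, and Section 8.1 sorts listings by subject and, where appropriate, by image. With 3 to 6 patients, uneven image counts could be seen there. A listing does not, however, say in advance which per-patient figure counts.
- **The contrast with SBR is partial.** SBR is averaged per patient for its two-sample and paired tests, where independence requires it. It is also analysed with image as a repeated factor and in separate image-analysis tables. No between-cohort test of the rating is planned.
- **The figures are illustrations.** They place the heavily imaged patient at the opposite extreme from the rest, and the effect is weaker at n = 6.
- **Images differ in kind.** Nerve diameter and overlying tissue vary, so a single figure per patient can hide poor visibility of a particular nerve. This is a reason to keep the image-level counts.

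A reader might infer that one patient could set a cohort's result and hence the dose. The documents do not support that. The SRC decides by judgement on safety and adequacy of fluorescence, SBR is assessed alongside the rating, and no rule is tied to a pooled rating percentage. A reader might also infer that the B1 versus B2 comparison is compromised. The planned test uses SBR averaged per patient, so only the descriptive rating summary for timing is exposed.

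**Conclusion.** The point holds as a weakness in a descriptive summary. A secondary endpoint that informs the dose choice has one stated unit, the image, and no stated per-patient summary, in cohorts where one patient with three times the images of each other would carry 60% (n = 3) or 37.5% (n = 6) of the figure. The direction of any distortion cannot be known in advance.

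The conclusion rests on two conditions. First, image counts must differ materially between patients, which the documents neither state nor exclude. Second, no rule on image numbers or per-patient display may exist in text that was not available: the protocol's design section, the separate specifications for tables, listings and figures cited in SAP Section 2.1, and a small part of the SAP. The change is worth making because it extends what the SAP already does for SBR and costs little.

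**What to change.** In SAP Sections 7.3 and 13.2 and in Table 14.2.5.1, add a prespecified per-patient summary of the rating by camera:

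- the patient's median rating, and the share of that patient's images rated 4-5 (a grouping that Section 13.1 already uses in its ROC analysis);
- both shown for each patient and summarised by cohort with equal weight per patient;
- the number of images per patient and camera.

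Keep the image-level counts alongside. State in Section 7.2 that the per-patient summary also serves the dose and timing objectives. Set no new threshold for adequacy: the purpose is to fix the unit of summary, and what counts as adequate stays with the SRC.

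The cost is some SAP wording and one extra table panel, with no new data. The downside is that a cohort's figure may look less favourable than the pooled one.

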## 8 General Statistical Methods and Definitions

### 8.1 General statistical methods

Summary tables will be structured with a column for each device and/or cohort.

The statistical analysis will be based on separate analysis populations, defined in section 4 Analysis Sets and Cohorts. Summary tables will usually be structured with a column for each cohort and the dose associated (ALM-488 100mg, ALM-488 XXXmg ...., ALM-488 XXXmg for Dose Escalation/De-Escalation, and as well as for Dose Timing. If dose modification occurs or if fluorescence signal has not been achieved after 6 dose cohorts the modified or the additional dose escalation cohorts will be presented on the tables.

Additional cohorts beyond dose cohort 6 may be enrolled if an adequate fluorescence signal has not been achieved after 6 dose cohorts have been evaluated. Additional dose escalation cohorts may be added following discussion with FDA if further improvement of fluorescence is needed for nerve identification and if the DLT rate is 0

In general, continuous variables will be summarised using descriptive statistics, i.e. generally displaying number of subjects in the respective analysis population, number of subjects with data, number of subjects with missing values, mean, standard deviation, minimum, lower quartile, median, upper quartile, and maximum.

Categorical variables will be summarised by using frequency counts and percentages. For events that can occur more than once, the number of events may also be summarized. In addition, the number of subjects with missing values will be displayed.

Means and medians will be presented by 1 additional decimal place and standard deviation will be presented by 2 additional decimal places than the standard presentation level of the respective data. Minimum and maximum values will be presented using the same number of decimal places as the data. Percentages will be presented to 1 decimal place if not otherwise stated.

If the number of subjects in a category is 0, then percentage will not be displayed, and only a count of 0 will be shown.

QMS Document Name: Statistical Analysis Plan	Page 13 of 29
QMS No (include version ref): STF-015-GL.02	Document date: 09JUL2019
CONFIDENTIAL	

P-values will be reported to 4 decimal places at least. Values less than 0.0001 will be displayed as <0.0001. Values above 0.9995 will be displayed as 1.0000.

In listings, data will be sorted by dose Cohort, site, and subject ID, and when appropriate by image, visit or other identifiers for sequence or type of observation.

Factor 365.2425 is used for duration conversions between days and years. Factor 30.436875 is used for duration conversions between days and months.

If not otherwise specified, all statistical tests will be two-sided, and confidence intervals will be two-sided and will be at the 95% confidence level.

## ***8.2 Covariates and strata***

No stratified analyses are planned for this study.

## ***8.3 Subgroups***

For the efficacy analysis, the subgroup of images with overlying tissue will be explored. In this subgroup, the depth will be measured via the amount of overlying tissue that there can be to still maintain the ratio of nerve to non-nerves. Other subgroup analyses will be presented by cohorts and by cameras (OnLume or Zeiss). Both cameras are able to capture WLR and FL lights.

Results for the different subgroups will be presented descriptively.

## ***8.4 Missing data***

Only observed data will be summarized for all Cohorts. Except for partial or missing dates, no imputation for missing data is planned for the summary or analyses of these study data.

The missing component(s) of incomplete dates (e.g. start and/or stop dates of AE, concomitant medication, medical history) will be assumed as the most conservative value possible. For example, if the start date has a missing day value, the first day of the month will be imputed for study day computations, etc. If day is missing for an end date, the last day of the month will be imputed. If the start date has a missing month value, the first month of the year will be imputed for study day computations, etc. If month is missing for an end date, the last month of the year will be imputed. For determination of treatment-emergent status, the start date will be imputed as the date of the first dose of study drug, unless there is clear evidence (through comparison of partial dates/times) to suggest otherwise.

Date imputation will only be used for computational purposes such as treatment-emergent status, etc. Actual data values, as they appear in the original eCRFs, will be presented in the subject data listings.

QMS Document Name: Statistical Analysis Plan	Page 14 of 29
QMS No (include version ref): STF-015-GL.02	Document date: 09JUL2019
CONFIDENTIAL	

